15.4 Missing, unused & spurious data

Participants with incomplete follow-up will enter the primary analysis following multiple imputation. Further detail will be provided in the Statistical Analysis Plan (SAP).

15.5 Procedures for reporting deviation(s) from the original SAP

These will be submitted as substantial amendments where applicable and recorded in subsequent versions of the protocol and SAP.

15.6 Termination of the trial

Progression criteria for the internal pilot phase are described in Section 6. There is the potential for the trial to terminate early if our funder assesses the trial as not being feasible following the assessment of progress against our targets at the end of the internal pilot with input from our TSC and IDMC.

15.7 Inclusion in analysis

All eligible participants who have been randomised will be included in the primary intention-to-treat analysis regardless of their treatment adherence, discontinuation, and initiation of the subsequent treatment as described in the primary estimand Section 16.1 below. As part of sensitivity analyses, ineligible participants will be excluded from the analysis, and alternative analysis populations (as described in Section 16.1) will be used.

16 Analysis

16.1 Main analysis

Descriptive statistics will be summarised using frequencies and percentages, means and standard deviations, or medians and interquartile ranges as appropriate. Recruitment, retention, and other trial processes (e.g. adherence to allocation) will be reported both overall, by arm, and disaggregated by site, menopausal status, previous UTI frequency, and previous type of failed treatment.

The primary analysis will be an intention to treat, including all randomised participants regardless of adherence or discontinuation of the initial treatment allocation or initiation of the subsequent treatment.

For the clinical-effectiveness primary outcome (rate of symptomatic, antibiotic-treated UTI, selfreported by participants from randomisation to the 6-month treatment period (verified from medical

Canolfan

records)), a Poisson/negative binomial regression model will be fitted to estimate incidence rate ratios, including fixed effects for allocation, covariate factors used in randomisation (prior frequency of UTI and menopausal status) and random effects to model heterogeneity between sites. Regression analysis results will be presented as point estimates with confidence intervals and p-values. The primary estimand for VESPER is below:

Primary clinical question: In women who fail first-line preventative treatment for rUTI, does the strategy to initially prescribe intravesical treatments result in a greater reduction in the rate of symptomatic UTIs over the subsequent 6 months compared to the current guideline-recommended second-line prophylactic antibiotic therapy?

The estimand is described by the following attributes:

- Population: women aged >16years with recurrent uncomplicated UTI who have failed firstline treatments requiring second-line prophylactic treatment and able to receive intravesical treatments and take second-line oral antibiotic prophylaxis.
- **Endpoint**: rate of symptomatic UTIs from randomisation to 6-months. •
- **Treatment condition**: The intravesical treatments and second-line oral antibiotic prophylaxis, regardless of adherence or discontinuation of the initial treatment allocation or initiation of the subsequent treatment (via re-randomisation) (treatment policy strategy);
- Remaining intercurrent events: Treatment adherence or discontinuation or initiation of the subsequent treatment are covered by previous attribute.
- Population-level summary: Incidence rate ratio from Poisson or negative binomial regression model for intravesical treatments and second-line oral antibiotic prophylaxis arms.

Rationale for estimand: To compare the strategy of initially prescribing intravesical treatments compared to prescribing second-line oral antibiotic prophylaxis as would be observed in routine practice.

Sensitivity analyses around the primary outcome will consider appropriate estimands, accounting for initial allocation and reinstatement/switching of different prophylaxes via the SMART design. Weighted and replicated regression approach will be considered to evaluating adaptive intervention effects³⁴.

Secondary outcomes will also be analysed based on intention-to-treat using appropriate regression models (e.g. linear regression for continuous outcomes, Poisson/negative binomial for counted outcomes, logistic regression for binary outcomes, as appropriate), adjusting for covariate factors

used in randomisation as per the primary analysis, and are described in the Table below. Mixed-effects models will be considered when participants have multiple data points over time.

As part of our process evaluation, we will describe differences between those who opt for different modes of intravesical administration (i.e. self vs clinician-delivered), including the extent to which it varies across sites. We will also describe the timing of this decision in relation to randomisation and whether this is associated with differential response, switching, and outcomes. We will similarly describe the variability (and association with response/outcomes) in prophylaxis implementation more generally (i.e. which oral antibiotics are used in the oral antibiotic arm, switches and circumstances around switching etc.)

Table 7 - planned outcome analysis

Outcome	Measure	Time frame	Analysis
Occurrence of symptomatic UTI in the 6-month follow-up period	UTI-rate occurred after 6 months of treatment period	At 12 months	Poisson/ negative regression
Change in rUTI Impact Questionnaire	Recurrent UTI impact questionnaire	At 6 months/12 months	Linear regression
Days prescribed antibiotics	Addition antibiotic prescribed	At 6 months/12 months	Poisson/ negative regression
Microbiologically proven UTIs	Per the primary outcome plus a concomitant positive urine culture	At 6 months/12 months	Logistic regression
AMR in E. coli isolated from urine or perineal swabs	Resistance to 1 or more antibiotics in the panel tested	At 6 months/12 months	Logistic regression
Multi-drug resistance in E. coli	Resistance to >=1 antimicrobial agent in >=3 antibiotic categories	At 6 months/12 months	Logistic regression
Asymptomatic bacteriuria	Positive urine culture without symptoms	At 6 months/12 months	Logistic regression

Canolfan

Adverse events	Type, frequency, and severity of adverse events	At 6 months/12 months	Descriptive statistics
Hospitalisation due to UTI	Number of hospitalisation due to UTI	At 6 months/12 months	Poisson / negative binomial regression
Quality of life	EQ-5D-5L	At baseline/3/6/12 months	Linear regression
Participant satisfaction	Treatment Satisfaction Questionnaire for Medication	At 6 months/12 months	Linear regression

A comprehensive Statistical Analysis Plan will be finalised by the trial statistician, with support from the Management Group (TMG), agreed by the Trial Steering Committee (TSC), and Data Monitoring and Ethics Committee (DMEC) prior to database lock and commencement of analysis. The findings will be reported in line with the Consolidated Standards of Reporting Trials (CONSORT) statement. We will incorporate the estimand framework within our protocol and statistical analysis plan, with the aim of specifying primary and sensitivity estimands and aligning analysis strategies accordingly. Our primary clinical analysis will be based on a "treatment policy" strategy of offering each of these options as second-line prophylaxis and analyse participants in the arm to which they were originally randomised within a multiple imputation framework, regardless of intravesical instillation/prophylactic oral antibiotics receipt (including treatment switching) or outcome availability.

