5.4 Secondary outcomes measure(s)

Secondary outcome measures include:

- Occurrence of symptomatic UTI in months 6-12 (following treatment completion)
- Psychosocial burden of rUTI using the rUTI Impact Questionnaire¹¹ at 6 months and 12 months

- Antibiotic use: number of courses of antibiotics prescribed for UTI
- Microbiologically proven UTIs: defined as per the primary outcome plus a concomitant positive urine culture (central laboratory). Participants will be requested to submit urine samples both locally and to the central laboratory when they suspect a UTI based on symptoms. A positive culture will be classified according to UK Health Security Agency (UKHSA) standards for Microbiological Investigations (SMI) B41: Investigation of urine definitions²⁵.
- AMR in *E. coli* isolated from urine or perineal swabs.
 - Ecological change in terms of bacterial species plus antimicrobial resistance patterns from i) mid-stream urine and ii) faecal reservoir (via optional perineal swabs) during the 6-month treatment period and in the 6 months following completion of treatment. Urine and optional perineal samples will be taken at hospital visits during both treatment and follow-up, plus participants will be requested to submit further urine samples to the central laboratory when they suspect a UTI based on symptoms. GP or hospital records will be checked to confirm any additional urine culture results, including resistance patterns of the bacteria cultured. We are planning to longitudinally monitor development of antimicrobial resistance in the primary uropathogen *E. coli* isolated from urine by collecting specimens sent by participants directly to our central reference laboratory at the time of each UTI and during asymptomatic periods at baseline, 1,3, 6 and 12 months. We will also assess resistance pattern change in *E. coli* within the faecal reservoir by obtaining isolates from perineal swabs sent at baseline, 6 and 12 months.
 - Multi-drug resistance in *E. coli* isolated from urine or perineal swabs, defined as resistance to >=1 antimicrobial agent in >=3 antibiotic categories
- Bacterial species or antibiograms most commonly associated with recurrent UTI.
- Asymptomatic bacteriuria defined as a positive urine culture without symptoms
- Adherence with allocated treatment (patient reported)
- Adverse events
- Hospitalisation due to UTI

• Costs to NHS and personal social services (PSS) at 12 months and modelled over participant lifetime

VESPER

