13.1.2 Baseline data collection

Baseline data collection will be undertaken at the participating site by an appropriately delegated member of the VESPER Trial team. Baseline data may be collected at the initial eligibility appointment or at a subsequent 'baseline' appointment (as described above).

- Demographics •
- **Registration form**
- Physical examination •
- Medical history •
- rUTI Impact questionnaire •
- UTI diary •
- EQ-5D-5L •
- Service use questionnaire •
- eGFR & LFTs (Blood samples) •
- Mid-steam urine samples
- Perineal swabs

Mid-stream urine samples and perineal swabs will be obtained and sent to the central laboratory.

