16.3.2 Outcomes

EQ-5D-5L

The EQ-5D-5L will be administered at baseline, 3-, 6- and 12-months post-randomisation. Responses will be converted into utility values using the UK recommended tariff⁴³. QALYs will be estimated using the area under the curve approach⁴⁴. In a sensitivity analysis the disutility associated with a UTI episode, estimated in a previous NIHR HTA study, will be considered in the QALY calculation³.

Willingness-to-pay to avoid a UTI

Despite considering the disutility associated with a UTI in a sensitivity analysis, given the short duration of UTIs, potential differences in quality of life associated with a reduction in UTIs may not be captured by QALYs. In a previous NIHR HTA study women were asked to value, in monetary terms, how much they would be willing-to-pay to avoid a UTI⁴¹. The average willingness-to-pay value estimated will be inflated to the current price year and combined with the number of UTIs reported by participants in VESPER⁴². This will be presented as the burden of UTIs reported in VESPER on women, in monetary terms, for each of the randomised arms.

Discrete choice experiment

To estimate women's preferences for the trial interventions and their associated outcomes, a discrete choice experiment (DCE) will be administered, to all participants, at month 13, so as to not affect the response rate for other trial outcomes. A DCE involves presenting individuals with a series of hypothetical alternative choice sets, usually pairwise, differing in their attributes and levels, and asking them to indicate their preferred alternative in each set⁴⁵. The key attributes and associated levels reflecting the features and outcomes of the interventions, and a cost attribute will be derived using a literature review, and consultations (likely in the form of interviews and focus groups) with both women and clinicians. Once the attributes and levels have been identified, the DCE will be designed in NGene⁴⁶. The responses to the DCE will be analysed using appropriate regression models, such as conditional logit models and mixed logit models. These regression models will allow us to predict the value and relative importance that participants place on the different attributes of each intervention⁴⁷. The inclusion of a cost attribute will allow us to estimate women's marginal willingness-to-pay for each of the interventions' attributes and the net benefit of the treatments can also be estimated⁴⁸.

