16.3.3 Within-trial analysis

For the within-trial analysis, costs and outcomes will not be discounted as the time horizon is 12months. The economic analysis will compare the interventions in terms of mean costs and effects to estimate cost-effectiveness. Differences in costs and effects will be estimated simultaneously using seemingly unrelated regression, which controls for observed (e.g., age, baseline costs and utilities) and unobserved individual characteristics⁴⁹. If one treatment is not dominant (i.e., less costly and more effective) then, for the cost-utility analysis the incremental cost per QALY gained at 12-months will be estimated; and the cost-benefit analysis will estimate the incremental net benefit.

Sensitivity analysis

To replicate the primary outcome, time horizon, a sensitivity analysis will be undertaken to estimate the incremental cost per QALY gained over the treatment phase (6-months). Only costs and utilities reported between baseline and the 6-month follow-up will be considered in this analysis.

Both deterministic (e.g., variation in unit costs) and stochastic, in the form of the bootstrapping technique, will be used to explore potential uncertainties in costs, effects and cost-effectiveness⁵⁰. This statistical impression will be presented as both cost-effectiveness acceptability curves (CEACs) and cost-effectiveness planes^{51, 52}. For the cost-benefit analysis statistical imprecision will be displayed as cost and willingness-to-pay planes and as the probability of an intervention being efficient (i.e., the probability that the benefit of the intervention is greater than the cost).

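### Secondary models name no baseline outcome value as a covariate, and Table 7 lists baseline as an EQ-5D-5L outcome time, although these values are collected before randomisation

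*Protocol*

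**What the plan says.** Section 16.1 of the protocol describes the primary model as adjusting for "covariate factors used in randomisation (prior frequency of UTI and menopausal status) and random effects to model heterogeneity between sites". For secondary outcomes it says the models adjust for the factors "used in randomisation as per the primary analysis, and are described in the Table below". No baseline value of any outcome is named. Mixed models for repeated measurements are left open.

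Table 7 then sets, row by row:

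- "Change in rUTI Impact Questionnaire", at 6 and 12 months, by linear regression;
- quality of life by EQ-5D-5L, "At baseline/3/6/12 months", by linear regression;
- asymptomatic bacteriuria at 6 and 12 months, by logistic regression.

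Each of the three has a pre-randomisation value:

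- Section 13.1.2 lists the "rUTI Impact questionnaire", EQ-5D-5L and mid-stream urine among the baseline data.
- Section 16.3.2 says "The EQ-5D-5L will be administered at baseline, 3-, 6- and 12-months post-randomisation".
- Section 5.4 plans urine specimens "during asymptomatic periods at baseline, 1,3, 6 and 12 months".
- Section 9.6.1 places all baseline data and samples before randomisation.

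The economic analysis in section 16.3.3, by contrast, uses a regression that "controls for observed (e.g., age, baseline costs and utilities").

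**The concern.** Three things follow if the secondary models are fitted as section 16.1 describes them.

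First, a change score or follow-up score without the baseline covariate is less precise than the collected data allow.

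Second, neither form removes chance baseline imbalance. A follow-up score carries part of it directly. A change score carries part of it with the sign reversed, through regression to the mean. The minimisation factors do not include the baseline score, and the oral arm is small (62 of 412), so a noticeable imbalance there is quite possible.

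Third, EQ-5D-5L is the only row of Table 7 with a pre-randomisation time in its time frame. No treatment effect can exist at baseline, so a model that counts it as an outcome time without separating it from the later times dilutes the effect.

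What is at stake is the precision of the trial's disease-specific patient-reported measure and its generic quality-of-life measure. The primary analysis of UTI rate is not touched.

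**Working it through.** The protocol gives no standard deviation, correlation or power for any secondary outcome, so there is no stated figure to reproduce.

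**Inputs**
- Arm sizes 62, 175 and 175, and 15% drop-out (section 15.3). Analysable: 0.85 × 62 = 53 and 0.85 × 175 = 149.
- Correlation r between baseline and follow-up, within arm and after the minimisation factors: not given. Assumed 0.3 to 0.7.
- Equal standard deviations at baseline and follow-up: assumed, set to 1.

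**Relative variance of an arm difference**
- Unadjusted follow-up score: 1
- Unadjusted change score: 2(1 − r)
- Baseline as covariate: 1 − r²
- Cut against the change score: 1 − (1 − r²)/[2(1 − r)] = (1 − r)/2
- Cut against the follow-up score: r²

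| r | Follow-up | Change | Baseline-adjusted | Cut v change | Cut v follow-up |
|---|---|---|---|---|---|
| 0.3 | 1.00 | 1.40 | 0.91 | 35% | 9% |
| 0.5 | 1.00 | 1.00 | 0.75 | 25% | 25% |
| 0.7 | 1.00 | 0.60 | 0.51 | 15% | 49% |

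As r rises, the gain shrinks for the questionnaire (change score) and grows for EQ-5D-5L (follow-up score). One figure cannot describe both.

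**The same result as power**, two-sided 5%. The arm sizes cancel, so this holds for either contrast.
- An effect with 80% power on the change score has 93.5%, 89.9% and 86.0% with baseline adjustment at r = 0.3, 0.5 and 0.7.
- An effect with 80% power on the follow-up score has 83.6%, 89.9% and 97.5%.

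**Chance imbalance, oral arm against one intravesical arm**
- Standard error of the baseline difference: √(1/53 + 1/149) = 0.16 SD.
- For a baseline difference of that size, the change score shifts by (1 − r) × 0.16 in the opposite direction: 0.11, 0.08 and 0.05 SD at r = 0.3, 0.5 and 0.7.
- The follow-up score shifts by r × 0.16 in the same direction: 0.05, 0.08 and 0.11 SD.
- With baseline as a covariate in the linear model, this shift is removed.

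**EQ-5D-5L with baseline as an outcome time**
- Suppose one treatment term, four equally weighted times, and a constant effect d at 3, 6 and 12 months. The expected estimate is (0 + d + d + d)/4 = 0.75d.
- With treatment-by-time terms and a common baseline mean this dilution does not occur.

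**Asymptomatic bacteriuria**
The formulas above are for linear models. In logistic regression, adding a baseline covariate changes which odds ratio is estimated as well as its precision, so no variance figure is given.

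**The case against.** The strongest reply is that covariates of secondary models are ordinary analysis-plan detail. The protocol promises a full statistical analysis plan, does not say that the named factors are the only ones, and leaves mixed models open. Adding a baseline covariate later would contradict nothing. A change outcome regressed on arm and baseline also gives the same treatment estimate as the baseline-adjusted follow-up score, so the label in Table 7 does not rule the better model out. Much of this stands, and it limits the weight of the point. It does not remove it: section 16.1 goes beyond silence by stating an adjustment set, and Table 7 states outcome form and times. As they read, these describe a less efficient analysis than the data allow.

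A reader might infer more than the protocol supports:

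- *That about a quarter of the variance is left in.* This holds only at an assumed correlation of 0.5, where the two formulas happen to agree.
- *That the EQ-5D-5L effect will be shrunk.* This needs a pooled single-term model that the protocol does not state. The table entry may simply repeat the collection schedule.
- *That the comparisons are biased.* Under randomisation the unadjusted change and follow-up comparisons are unbiased on average. The loss is precision, and exposure to the imbalance that happens to occur.
- *That the economic analysis contradicts Table 7.* Section 16.3.3 concerns costs and effects measured as QALYs, which is a different endpoint from EQ-5D-5L scores. It shows that baseline utility is available and thought worth adjusting for, and no more.

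**Conclusion.** The point holds as a worthwhile improvement to secondary outcomes. As written, section 16.1 and Table 7 describe patient-reported comparisons that are less precise than they could be and that carry chance baseline imbalance. The baseline entry in the EQ-5D-5L row is at best ambiguous.

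The size rests on an assumed correlation of 0.3 to 0.7 and on equal standard deviations. The direction does not depend on the value chosen: with equal standard deviations, the adjusted analysis beats the change score at every correlation below 1, and beats the follow-up score at every non-zero correlation. The three-quarters figure for EQ-5D-5L is conditional on the pooled model. For bacteriuria the case is only that a plausible prognostic value is collected and not named.

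**What to change.** In section 16.1, say that secondary models also include the baseline value of the outcome where it is collected. In Table 7:

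- rUTI Impact Questionnaire: model the 6- and 12-month scores with the baseline score as covariate. The treatment estimate also answers the change question.
- EQ-5D-5L: give the outcome times as 3, 6 and 12 months, adjusted for baseline. Alternatively, state a mixed model with treatment-by-time terms and a common baseline mean.
- Asymptomatic bacteriuria: add baseline bacteriuria (yes/no) as a prognostic covariate.

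Carry the same wording into the statistical analysis plan, with a simple rule for the few missing baseline values. The cost is a few lines of text. No new data are needed, and the sample size and primary analysis are unchanged.

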analysis identified no randomised trials (RCTs) of intravesical antibiotics and two small RCTs for intravesical GAG replacement compounds (n=26, n=54)⁹. Despite this paucity of high-level evidence our recent survey conducted via the UK Continence Society found that 76% of specialists regularly use intravesical treatments in their everyday practice. There appears to be a significant disparity between the widespread clinical use of these treatments and the evidence required to justify this. A recent overview in this topic area highlighted the use of intravesical preventative treatments as a potential future therapy and stated that "high local concentrations of antibiotic at the urothelial surface can be achieved by direct instillation into the urinary tract". The authors noted that "only the performance of clinical trials in the appropriate patient populations can properly appraise the potential of intravesical therapy for UTI"¹⁰. There is clearly an urgent need for a well-designed trial to demonstrate the relative effectiveness of the 2 most commonly used intravesical treatments and compare this to the current guideline-recommended treatment of second line daily oral antibiotics. VESPER, a 3-arm RCT designed to assess the relative effectiveness and cost-effectiveness of two intravesical preventative treatments, Gentamicin and GAG replacement compounds, against guidelinerecommended second-line daily oral tablet antibiotic prophylaxis will directly address this evidence gap. Secondary outcomes will include development of antimicrobial resistance (AMR) during treatment, total antibiotic use, patient-reported treatment satisfaction, patient-reported UTI impact¹¹, adverse events and, using economic analysis, the value of the interventions to women suffering rUTI and to the NHS.

4.1 **Rationale for current trial/Justification of Treatment Options**

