5.3 Primary outcomes measure(s)

The primary clinical effectiveness outcome is the rate of symptomatic, antibiotic-treated UTI, selfreported by participants from randomisation to the 6-month treatment period (verified from medical records).

The primary economic outcome is the incremental cost per quality-adjusted life year (QALY) gained, based on responses to EQ-5D-5L, over 12 months.

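### Table 7 does not analyse two secondary outcomes as section 5.4 defines them: culture-proven UTIs are defined from a rate but get logistic regression, and antibiotic use changes from courses to days

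*Protocol*

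**What the plan says.** **Proven UTI.** Section 5.3 sets the outcome on which the definition rests: "The primary clinical effectiveness outcome is the rate of symptomatic, antibiotic-treated UTI, selfreported by participants from randomisation to the 6-month treatment period". Section 5.4 then has "Microbiologically proven UTIs: defined as per the primary outcome plus a concomitant positive urine culture (central laboratory"), and Table 7 repeats this as "Per the primary outcome plus a concomitant positive urine culture", to be reported at 6 and 12 months by logistic regression. The text above the table gives the rule for choosing a model: "Poisson/negative binomial for counted outcomes, logistic regression for binary outcomes, as appropriate". For the primary outcome, section 16.1 says "a Poisson/negative binomial regression model will be fitted to estimate incidence rate ratios".

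**Antibiotic use.** Section 5.4 lists "Antibiotic use: number of courses of antibiotics prescribed for UTI". The matching row of Table 7 is headed "Days prescribed antibiotics". Its measure column refers only to additional antibiotic prescribed, with no unit and no restriction to UTI, and its model is Poisson/negative binomial. Table 7 has no row for courses. Section 4 (Background) summarises the plan in a third way: "Secondary outcomes will include development of antimicrobial resistance (AMR) during treatment, total antibiotic use".

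**The concern.** The protocol fixes both the definition and the analysis of each outcome, and they do not match. This is therefore not detail left to the statistical analysis plan.

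For proven UTI, a woman with one culture-proven infection and a woman with four would count the same in a logistic model of any event. The estimate would be an odds ratio, while the primary outcome gives a rate ratio. That matters because the trial is open label and the primary outcome is self-reported, although verified from medical records. A central-laboratory culture result is a natural check on it, and the check is most useful on the same scale.

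For antibiotic use, courses and days answer different questions. A reader of the results could not tell which of the two was the pre-specified outcome.

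**Working it through.** The plan states no figure to reproduce here. The main check is a comparison of the text, and the arithmetic only shows what the choice of model can change.

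**1. Proven UTI, text compared**
- Section 5.3: the primary outcome is a rate.
- Section 5.4: proven UTI is that outcome plus a positive culture, so it is also a rate or count of events.
- Section 16.1: counts get Poisson/negative binomial, and binary outcomes get logistic.
- Table 7: proven UTI gets logistic. The other two UTI event rows (symptomatic UTI in the follow-up period, and hospitalisations due to UTI) get the count model.
- No section defines a variable such as at least one proven UTI.

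The row therefore conflicts with section 5.4 and with the protocol's own rule.

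**2. Antibiotic use, text compared**
- Section 5.4: the unit is a course, prescribed for UTI.
- Table 7: the unit is a day.
- With illustrative lengths, a 7-day and a 3-day course each count as 1 course, but as 7 and 3 days.

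**3. Illustration for proven UTI at 6 months**

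Inputs from section 15.3:
- Rates of 2 (oral) against 1 (intravesical).
- Rates of 1 against 0.7 for the 30% head-to-head difference.
- 62 oral participants and 175 in each intravesical arm, with 15% drop-out: 62 × 0.85 = 52.7, taken as 53; 175 × 0.85 = 148.75, taken as 149.

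Assumptions not in the protocol:
- The rates apply per 6 months (section 15.3 gives no time unit).
- There is no overdispersion.
- A share *f* of UTIs is culture-proven, with *f* = 30%, 50% or 70%, equal across arms.

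Formulas, with means m₁ and m₂ equal to *f* times the rates, and two-sided α = 0.05:
- Count model: power = Φ( ln(m₁/m₂) / √[1/(n₁m₁) + 1/(n₂m₂)] − 1.96 ).
- Any event: p = 1 − exp(−m), then power = Φ( (|p₁ − p₂| − 1.96·SE₀) / SE₁ ), with SE₀ from the pooled proportion and SE₁ from the separate ones.

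Worked case, head-to-head at *f* = 70%: m = 0.70 and 0.49.
- Count: the standard error is √[1/(149 × 0.70) + 1/(149 × 0.49)] = 0.153, and ln(1/0.7) = 0.357. The ratio is 2.34, so power is Φ(0.38) = 65%.
- Any event: p = 0.503 and 0.387, giving 52%.

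| Comparison | *f* | Count model | Any event | Rate ratio | Odds ratio |
|---|---|---|---|---|---|
| 1 v 0.7, 149 v 149 | 30% | 33% | 30% | 1.43 | 1.50 |
| | 50% | 51% | 43% | 1.43 | 1.55 |
| | 70% | 65% | 52% | 1.43 | 1.60 |
| 2 v 1, 53 v 149 | 30% | 85% | 73% | 2.0 | 2.35 |
| | 50% | 97% | 86% | 2.0 | 2.65 |
| | 70% | over 99% | 91% | 2.0 | 3.01 |

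The loss is about 3 to 13 percentage points. The odds ratio moves with the culture-proven share while the rate ratio does not, so the two scales cannot be read across directly.

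**The case against.** The strongest reply is that logistic regression on at least one proven UTI is a legitimate analysis, that the text allows models as appropriate, and that the outcomes are secondary. The first part is true in principle, but the protocol never defines that binary variable. The latitude in the text does not help either, because Table 7 names the model and the stated rule points to the count model for a rate. The last part stands: nothing here touches the primary analysis or the sample size.

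Three stronger readings are tempting, and the documents do not support them.

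- **A severe loss of power over 12 months because nearly every woman has an event.** This needs all UTIs to be culture-positive, planning rates that are per 6 months and persist after treatment stops, and counting that accumulates over 12 months. The protocol states none of these. Section 5.4 treats months 6–12 as a separate window for symptomatic UTI, and section 15.3 describes the patient-derived target as one episode per year. Even on those inputs (98% oral against 86% intravesical with an event), the two-proportion formula gives 74% power. A Wald formula on the log odds ratio gives 52%, but it is unreliable with about one expected non-event in the oral arm (53 × 0.018 = 0.97).
- **About 180 prophylaxis days in the oral arm decide the ranking of the arms.** Section 5.4 restricts the outcome to antibiotics for UTI, and Table 7 refers to additional antibiotic. Both point to leaving allocated prophylaxis out. The phrase in section 4 is a background summary, not an outcome definition.
- **Standard errors for days will be too small under Poisson.** The same row already offers the negative binomial, and choosing between the two is ordinary content for the analysis plan.

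**Conclusion.** Both mismatches hold on the text alone, without any assumption. For proven UTI, Table 7 applies a binary model to an outcome defined from a rate. The cost is the loss of repeat events and a change from rate ratio to odds ratio. For antibiotic use, section 5.4 and Table 7 name different outcomes.

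The size of the power loss is less certain than the mismatch. The range of about 3 to 13 points rests on rates per 6 months, 15% drop-out, no overdispersion and an assumed culture-proven share of 30–70%. If the rates are annual, the 6-month means halve. A 60% share would then give the 30% rows of the table (0.60 × 0.5 = 0.30), where the head-to-head loss is about 3 points and the oral comparison loses about 12. This should be corrected, as a matter of making the plan agree with itself.

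**What to change.** In Table 7:
- **Proven UTI:** make the measure the number of culture-proven UTIs, analysed with the same Poisson/negative binomial model as the primary outcome and reported as an incidence rate ratio.
- **Antibiotic use:** make the measure the number of treatment courses for UTI, as in section 5.4. If days are kept, list them as a separate measure in both section 5.4 and Table 7, and state that allocated prophylaxis is excluded.

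The cost is a wording change in the protocol, carried into the statistical analysis plan. No new data are needed: section 11.1 already provides for recording the agent and duration of every treatment course, and participants are already asked to send urine to the central laboratory at each suspected UTI. The change is best made before database lock, because in an open-label trial a later change of outcome or model could look driven by the data.
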